9.4 Data sources

All data sources are nationwide registers in native format. All study investigators have access to their country-specific data and can link data between registers for the purpose of our study. Given the near real-time availability of the data source, our analyses will provide timely evidence. Denmark and Finland will have full data availability for all variables (with no missing data; all the exposures, outcomes, or covariates are either present or not) during the study period and as reporting to national registers is mandatory/structurally implemented, this provides complete follow-up of all residents over time. Currently, Sweden has limited access to nationwide influenza vaccination data but will be able to provide data from four regions in Sweden with a combined population of 1,220,00 individuals. These include Uppsala Region (405,000), Jönköping Region (370,000), Blekinge Region (160,000), and Värmland Region (285,000).

Table 7. Overview of individual-level data sources in the three Nordic countries

Country	Data sources						
Denmark							
Title	Info	Type	Setting	Study availability	Update	Lag	Ref
The Danish Civil Registration System	The register provides the unique personal identifier for all permanent residents of Denmark that allows linkage between all Danish health care registers and civil registrations systems. In addition, it holds general demographic information such as birthdate and sex as well as continuously updated information and dates on historical addresses, immigration and emigration status, and death.	Register	Nationwide	1968- today	Daily	No lag	(24)

The Danish vaccination register	The register holds information on all vaccinations given in Denmark including information on vaccination date, brand, type, dose, and product batch number ever since November 15, 2015 (when reporting to the register became mandatory).	Register	Nationwide	2020 – today	Daily	No lag	(25)
The National patient registry	The register covers all hospital contacts/visits in Denmark with information on the duration of the contact/visit, department of admission and other hospital characteristics. Treating physician-assigned diagnoses have been registered according to ICD-10 codes since 1995.	Register	Nationwide	1995 - today	Daily	No lag	(26)
The Danish Microbiology Database	Information on positive results of RT-PCR tests for influenza are obtained from The Danish Microbiology Database (MiBa) which holds information on all microbiology samples analysed at Danish departments of microbiology, including information on influenza test results, date of sampling, date of analysis, type of test and interpretation of the test (positive / negative).	Register	Nationwide	2020 – today	Daily	No lag	(27)

Country	Details of the individual-level data sources						
Finland							
Title	Info	Type	Setting	Study availability	Update	Lag	Ref
Finnish Population Information System	The register is held by the Digital and Population Data Services Agency and contains personal data on all permanent residents in Finland such as the unique personal identifier, date of birth, place of residence, date of death, and date of immigration, and emigration.	Register	Nationwide	1964 - today	Daily	No lag	(28)
National Vaccination Register	The register, which is based on the Register of Primary Health Care Visits, holds information on almost all influenza vaccinations administered in Finland; only influenza vaccinations given by social care givers such as nursing homes might be incompletely covered. Data include the date of vaccination, vaccine batch number and trade name.	Register	Nationwide	2009 - today	Daily	No lag	(29)

Care Register for Health Care	The register comprises information on all in-hospital care (since 1969) and outpatient specialist care (since 1998) in Finland, including admission and discharge dates, whether hospitalisation was planned or acute, codes for discharge diagnoses (according to ICD-10) and surgical procedures, whether discharged as deceased, to own private residence or other health care facilities, type of department and hospital. The register is held by the Finnish Institute for Health and Welfare.	Register	Nationwide	1967 - today	Daily	1-4 weeks	(30)
Register for Primary Health Care Visits	The register is held by Finnish Institute for Health and Welfare and holds data on all primary health care services delivered in Finland.	Register	Nationwide	2011 - today	Daily	No lag	(31)
National Infectious Diseases Register	The register contains information on notifiable diseases which must be reported by the laboratories and the physician treating the patient, or performing an autopsy, in accordance with the Finnish Communicable Diseases Act. All laboratory-confirmed influenza infections are recorded in the National Infectious Diseases Register. The register is held by the Finnish Institute for Health and Welfare.	Register	Nationwide	1995 - today	Daily	0-1 weeks	(32)
Special Reimbursement Register and Prescription Centre database	The Special Reimbursement Register holds information on individuals entitled to special reimbursement for medical expenses. The Prescription Centre database holds information on individuals using selected medications of interest. These databases are maintained by the Finnish Social Insurance Institution.	Register	Nationwide	1995 - 2023	Every 6 months	0-6 months	(33)
Finnish Intensive Care Consortium's Quality Register for Intensive Care	The register includes all intensive care admissions with primary diagnosis (ICD-10).	Register	Nationwide	2020 - today	Daily	No lag	(34)

Country	Details of the individual-level data sources						
Sweden							
Title	Info	Type	Setting	Study availability	Update	Lag	Ref

Swedish vaccination register	The register will contain information on administered influenza vaccines including data on the date of administration, the specific vaccine products, substance, formulation, batch number and dose number (for repeated doses). The register is held by the Public Health Agency of Sweden.	Register	Nationwide	2026-onwards	Daily	No lag	(35)
Regional vaccination data	Regional data contains information on administered influenza vaccines including data on the date of administration, and the specific vaccine products.	Regional data	Regional	2020-	Ad hoc		
Swedish national inpatient register	The register comprises information on all in-hospital (since 1987) and out-patient (since 2001) specialist care in Sweden including data on admission and discharge dates, whether hospitalisation was planned or acute, codes for discharge diagnoses and surgical procedures, whether discharged as deceased, to own private residence or other health care facilities, type of department, and hospital. For the current study period discharge diagnoses were recorded according to the Swedish clinical modification of the ICD-10 (i.e. ICD-10-SE). The register is held by the National Board of Health and Welfare.	Register	Nationwide	2017 - today	Monthly	2-4 weeks	(36)
Swedish Prescribed drug register	The Swedish Prescribed Drug Register contains details of all the prescriptions dispensed in Sweden since July 1, 2005. It is updated monthly with around 100 million prescriptions dispensed each year. It covers the entire Swedish population and includes information on unique personal identifier of the patient, age, sex, place of residence, and prescription information on substance, brand name, formulation and package dispensed amount, dosage (in free text) and unique expenditure and reimbursement, date of prescribing and dispensing, practice that has issued the prescription, and prescriber's profession. Drugs are identified by a unique identifier for each specific combination of brand name, substance, formulation, and package. Additionally, all drugs are classified according to the Anatomic Therapeutic Chemical Classification System (ATC). The register only includes filled prescriptions, not medicines sold over the counter, nor medicines administered directly by health-care personnel without prescription. The	Register	Nationwide	2017	monthly	2 weeks	(37)

	register is held by the National Board of Health and Welfare.						
Register on Surveillance of Notifiable Communicable Diseases (Sminet)	The register contains information on notifiable diseases (for which reporting is mandatory) reported by either the analysis-performing laboratories, the treating physician or the autopsy-performing physician, in accordance with the Swedish Communicable Diseases Act. Data include the date of disease occurrence, date of testing, date of positive test and diagnoses. The register is held by the Public Health Agency of Sweden.	Register	Nationwide	2020 - today	Daily	No lag	(38)

Missing data

There are no missing data in this study. All the exposures, outcomes or covariates are either present or not.

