9.2 Setting

Within Denmark, Finland, and Sweden, we will include all individuals aged 65 years and above, and individuals below 65 years of age at high risk of adverse influenza outcomes, who are known residents. We will analyse each target group in separate cohorts in each country.

Eligibility criteria for study inclusion are:

- 1) Individuals 65+-years-of-age (trial 1)
- 2) Individuals in risk groups 18-64-yrs-of-age (trial 2)
- 3) Have a known residency within the specific country at start of study period

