9.3 Variables

Exposures

The Nordic countries conduct annual influenza vaccination campaigns that focus on specific population groups at high risk of severe outcomes from influenza. These groups generally include the elderly, individuals with chronic health conditions, pregnant women, children and healthcare workers (Table 2).

The vaccines are provided free of charge and are typically administered before the peak flu season. In Denmark, vaccines for season 2024/2025 are administered from October 1st, in Finland from September 30th and in Sweden from October 15th. In immunization programmes across the three Nordic countries, the most frequently used quadrivalent inactivated influenza vaccine brands have been InfluvacTetra, VaxigripTetra, FluadTetra, FluarixTetra, and Efluelda Tetra, which are formulated

according to WHO's recommendations. The vaccines contain both seasonal influenza A subtypes, A(H3N2) and A(H1N1) pdm09, and both influenza B lineages, B/Victoria and B/Yamagata. Overview of the country-specific vaccine brands, types and target populations is provided in Table 3. At vaccination at general practitioners, regional vaccination centres or workplaces, individuals are vaccinated with the influenza vaccine available at the location.

An individual is defined as vaccinated starting from and including the day of the first influenza vaccination during the ongoing season, and as unvaccinated if they have yet to receive a first vaccine in the ongoing season.

Table 2. Influenza Vaccination Recommendations in Nordic Countries for season 2024/2025

Country	Target Groups for Influenza Vaccination

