9.5 Study size

Below we describe key target group sizes, vaccination coverage and recorded influenza infection incidences in the three Nordic countries for the 2023-2024 season. This provides a good indication of the possible study size for the 2024-2025 season. We expect to include at least 3.2 million individuals who are included in the key target groups for seasonal influenza vaccination across the 3 Nordic countries.

In Denmark, the total population of individuals aged 65 years and older, along with the population at increased risk below 65 years of age, consisted of 1,211 million and 554,780 individuals, respectively, as of 20 December 2024. (39) From 1 October 2024 to 20 December 2024, influenza vaccination coverage in these target groups was 75.6% and 29.2%, respectively. (39) As of 13 January 2025, there were 700 confirmed cases of influenza, including 414 hospitalisations, in older adults above 65 years. (40)

In Finland, the total population of individuals aged 65 years and older was 1,315 million with a vaccine coverage of 61% during the 2023-2024 season. The population at increased risk aged between 18 and 64 years comprised of 0,52 million individuals. The influenza A incidence was 65.5 per 10,000 person-years, and influenza A hospitalisation incidence was 5.4 per 100,000 person-years. As of 20 January 2025, there were 3224 confirmed cases of influenza in the Finnish population, including 81 hospitalisations due to influenza in adults aged 65 years and above. (41,42)

In Sweden, the total population of elderly 65 years and above in the four regions under study comprise of 280,000 individuals, with national influenza vaccination coverage of 69% in the 2023/2024 season. (43)

We will utilize all available data to us from the countries' nationwide registers (Denmark and Finland), and regional data sources (Sweden). The statistical power of our proposed study will be reflected in the 95% CI of the effectiveness estimates. We expect to have robust statistical precision for the most widely used influenza vaccine brands within the current season. (44,45)

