9.7 Data analysis

Procedures

We will use a matched cohort design to evaluate the effectiveness of seasonal influenza vaccine in comparison with not receiving a seasonal influenza vaccine. Individuals who have received the vaccine will be matched on the day of vaccination with individuals who have not yet received the vaccine. Individuals will be matched on age (5-year bins), sex, region of residence, and selected comorbidities. The day the seasonal vaccine dose was administered within each matched pair will serve as the index date for both individuals. If individuals who were included as a matched non-vaccinated individual

(i.e., a reference individual) receive a vaccine later than the assigned index date, the pair will be right-censored on the day the non-vaccinated individual is vaccinated. In these cases, the non-vaccinated individuals will be allowed to potentially re-enter as vaccine recipients in a new matched pair on that given date.

Statistical analysis

We will follow individuals from day 14 after the index date (to ensure full immunisation) up until the day of an outcome event, death, emigration, or end of the study, whichever occurs first. Additionally, we will censor individuals with a positive PCR test for influenza in our follow-up period 14 and 30 days after the test (as a positive test will be part of the outcome definitions) for the influenza hospitalisation and death outcome analyses, respectively. We will right-censor matched pairs when the reference unvaccinated individual receives a vaccine during follow-up. Cumulative incidences will be estimated by the Aalen-Johansen estimator, and from these we will calculate the comparative VE as $1 - \text{risk ratio}$ at the start of week 18 (depending on data availability) since index date. The corresponding 95% CI will be calculated using the delta method. Country-specific estimates will be combined by random-effects meta-analyses implemented using the *mixmeta* package in R.

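### Finnish exposure data are declared complete, yet Table 7 says nursing-home vaccinations may go unrecorded; residents can become misclassified controls, with bias in either direction and of unknown size

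*Protocol*

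**What the plan says.** Section 9.4 makes two statements about completeness. Its opening text says "Denmark and Finland will have full data availability for all variables", and its paragraph on missing data extends this to the whole study: "There are no missing data in this study. All the exposures, outcomes or covariates are either present or not".

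Table 7 in the same section describes the Finnish National Vaccination Register as holding nearly all influenza vaccinations, with one exception: "only influenza vaccinations given by social care givers such as nursing homes might be incompletely covered".

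The rules that turn a register record into a study arm are these:

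- Section 9.3 classifies a person "as unvaccinated if they have yet to receive a first vaccine in the ongoing season". In register data, that means no recorded dose.
- Section 9.2 asks for residency and target-group membership only: "Have a known residency within the specific country at start of study period". Residents of institutions are eligible.
- Section 9.7 says "Individuals will be matched on age (5-year bins), sex, region of residence, and selected comorbidities". Section 9.3 defines the comorbidity factor as a count of six conditions. Neither residence type nor frailty is a matching factor.
- Section 9.7 censors a pair when its unvaccinated member is vaccinated. In practice this needs a record.

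**The concern.** The completeness statements and Table 7 cannot both hold for Finnish exposure. The possible gap is also not spread evenly: it falls on people in social care.

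The error runs one way, because only vaccinated people are relabelled. A resident whose dose was not recorded stays in the pool of potential controls and can be paired with a vaccinee living in the community. Late vaccinees with a record end their pair's follow-up, whereas a mislabelled resident does not. The mislabelled share of control person-time can therefore grow toward week 18.

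Table 8 in section 9.8 already lists lower vaccination propensity in frail people as a source of overestimated VE against hospitalisation and all-cause mortality. Under-recording in nursing homes could produce that pattern as an artefact of the data.

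At stake are the Finnish 65+ estimates for hospitalisation and death and their contribution to the pooled results. Table 3 directs Fluad Tetra in Finland at people aged 85 and over, among others. If institutional residence is most common at those ages, which the Protocol does not state, that brand's Finnish estimate is the most exposed.

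**Working it through.** The Protocol states no figure for this bias, so there is none to reproduce. The check is whether the mechanism moves VE, and in which direction.

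**Input from the Protocol.** Finnish coverage at age 65 and over is 61% (section 9.5: "In Finland, the total population of individuals aged 65 years and older was 1,315 million with a vaccine coverage of 61% during the 2023-2024 season", where the comma is a decimal sign).

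**Assumed inputs, for illustration only.**
- p: share of residents in a matched stratum, 3% or 10%.
- c: true coverage in homes, 61% or 80%.
- s: share of home vaccinations recorded, 100% down to 0%.
- k: risk of an unvaccinated resident relative to an unvaccinated person in the community, 1 to 5.
- True VE: 40% or 0%, the same in both groups.

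**Model.** Community risk without vaccine is set to 1. It is a static mixture that ignores censoring.
- Mean risk, recorded vaccinated: Rv = (1 − VE) × [0.61(1 − p) + k·p·c·s] / [0.61(1 − p) + p·c·s]
- Mean risk, recorded unvaccinated: Ru = [0.39(1 − p) + k·p(1 − c) + k(1 − VE)·p·c(1 − s)] / [0.39(1 − p) + p(1 − c) + p·c(1 − s)]
- Observed VE = 1 − Rv/Ru

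**Worked case:** p = 10%, c = 61%, s = 50%, k = 3, true VE 40%.
- Rv = 0.6 × (0.549 + 0.0915)/0.5795 = 0.663
- Ru = (0.351 + 0.117 + 0.0549)/0.4205 = 1.244
- Observed VE = 1 − 0.663/1.244 = 46.7%

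**Observed VE with c = 61% and s = 50%:**

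| p | k | true VE 40% | true VE 0% |
|---|---|---|---|
| 3% | 1 | 39.4% | 0.0% |
| 3% | 3 | 42.6% | 6.7% |
| 3% | 5 | 45.3% | 12.2% |
| 10% | 1 | 38.2% | 0.0% |
| 10% | 3 | 46.7% | 16.9% |
| 10% | 5 | 52.1% | 27.1% |

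With complete capture and equal coverage, the model returns the true VE.

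**Direction.** A mislabelled resident has risk k(1 − VE), against 1 for an unvaccinated person in the community. Such residents raise the control risk above the community level when k > 1/(1 − VE). That is 1/0.6 = 1.67 at a VE of 40% and 1.0 at a VE of 0%. In the full model with equal coverage, observed VE passes 40% already at k of about 1.3, because the lost records also remove high-risk people from the vaccinated arm. At k = 1.5 with p = 10% and s = 50%, it is 1 − 0.616/1.039 = 40.7%. The simple threshold is therefore slightly conservative.

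**Dependence on coverage in homes.** With c = 80%, p = 10%, k = 3 and true VE 40%, observed VE is 32.1% at full capture, 36.2% at s = 80%, 42.0% at s = 50% and 51.2% at s = 0. Here the lost records first offset a downward bias and then exceed it.

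**The case against.** A reader might infer that Finnish VE against death and hospitalisation is overestimated, and might attach a figure. Suppose 2–3% of people aged 65 and over live in homes, 30–50% of their vaccinations are unrecorded, and mislabelled residents carry 5–10 times the risk of other controls after any vaccine effect. Their share of the control pool is then 0.00366/0.39366 = 0.93% to 0.00915/0.39915 = 2.29%. Dividing 0.6 by the inflated control risk turns a true 40% into 1 − 0.6/1.037 = 42% up to 1 − 0.6/1.206 = 50%. The documents do not support this reading, for three reasons.

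- The calculation fixes the vaccinated arm at 0.6 and sets coverage in homes to the general 61%. In the two-arm model with 80% coverage in homes, 2–3% residents and 30% unrecorded, observed VE is 38.9–39.7% for every k from 1 to 16.7, slightly below the truth.
- A ratio of 5–10 after vaccine effect means 5/0.6 = 8.3 to 10/0.6 = 16.7 before it, within strata already matched on age bin, sex, region and comorbidity count. Nothing in the Protocol supports such values.
- Table 7 describes a possible gap, not a measured one.

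Finland's weight can also be overstated. It has the largest 65+ population (1.315 million, against 1.211 million in Denmark and 280,000 in the Swedish regions). But section 9.5 reports 81 Finnish influenza hospitalisations at age 65 and over by 20 January 2025, against 414 in older Danish adults by 13 January. For that outcome Finland's weight in the pooled estimate may be modest.

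Finally, section 9.8 has general safeguards: the negative control outcomes, the prior event rate adjustment and the check of vaccination prevalence against national surveillance. The first two could reveal a frailer control arm. None can attribute it to unrecorded doses, and the test-negative analysis is Danish only.

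These arguments remove the claim of a known direction and size. They leave the contradiction and the mechanism in place.

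**Conclusion.** The point holds as a false completeness statement together with an unaddressed possible misclassification of Finnish exposure. It follows from the Protocol's own text that a vaccinated resident without a record can enter the control arm and stay there. Section 9.9 does not mention this, and no planned analysis isolates it.

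The direction is conditional. VE is biased upward if residents' excess risk outweighs their vaccine protection, roughly k above 1/(1 − VE). That is most plausible for death and severe outcomes and in the oldest age bins. Otherwise the bias is toward zero, and higher true coverage in homes can offset an upward bias. The size cannot be stated, because the share of residents, their coverage, the capture rate and their excess risk are all absent from the Protocol. The figures above show only that the shift may be under one percentage point or more than ten, depending on those assumptions.

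**What to change.** 1. Correct both completeness statements in section 9.4 to say that Finnish vaccinations given in nursing homes and by other social care providers may be unrecorded.
2. List exposure misclassification in section 9.9, with its conditional direction.
3. Keep the main analysis. Prespecify a Finnish 65+ sensitivity analysis for hospitalisation and mortality that excludes identifiable institutional residents from both arms, and report the pooled result with that estimate substituted.
4. If residents cannot be identified, prespecify a quantitative bias analysis over a range of capture rates instead.

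The cost is two corrected statements, one limitation and a little more analysis. Identification may be incomplete: Table 6 gives Finnish residence only by municipality, and the discharge destination in the Care Register covers only people who have been discharged from care. For that reason, and because restriction would make the Finnish target population differ from the Danish and Swedish ones, the restricted estimate is better kept as a sensitivity analysis than made the main pooled input.
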